### *Consenting and data collection with Intervention participants*

Consent forms will be completed with intervention participants in an in-person meeting. Baseline surveys will also be conducted by NYU study staff with intervention participants within two weeks after consent. (See *CHW Participant Baseline Survey*). A CHW Participant Followup Survey will be completed with intervention participants approximately six months after the start of intervention in order to evaluate the effectiveness of the CHW intervention.

Participants enrolled during the COVID-19 pandemic will be asked questions on vaccine hesitancy and COVID19 vaccination; as well as questions on mental health and mobile/technology use in order to understand how participants' chronic conditions and mental health was affected in during the pandemic and to understand how best to tailor remote intervention strategies to encourage vaccination among patients with overweight and pre-diabetes who are at higher risk for complications from COVID-19.

The CHW intervention includes a protocol that consists of 5 monthly 90-minute group health education sessions, providing the tools and strategies to prevent diabetes. All sessions employ adult learning techniques and group-based learning and activities. All session materials have been culturally and linguistically adapted into Bengali, Urdu, Hindi, Punjabi, and Nepali. Sessions will be held in remotely via audio phone calls via telephone, MCIT NYU approved Webex and Zoom platform or in community spaces identified by partner agencies, and multiple sessions will be held weekly to accommodate patient's varying schedules. Links to the health education sessions will be created via NYU approved Webex and Zoom platforms that are provided for use across the institution. These NYU Webex and Zoom links will be shared to participants via text message through NYU MCIT secured phones(see Text Message Script). The study team has developed training materials on how to use the NYU Webex and Zoom platforms to provide to research participants. Use of the Zoom will be used solely for the purpose of delivering the health education materials and will not involve discussion of PHI. In order to maintain anonymity for Zoom, for each session, the study staff will create Zoom waiting rooms for participants to be renamed as "Participant 1, Participant 2, etc.) prior to individuals joining the larger session with other research participants.

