In addition to these group sessions, patients will receive up to 9 follow-up phone calls from CHWs, during which individualized challenges, strategies, and action plans for improving diet and physical activity will be discussed (See Action Plan, *Progress Note Form for CHW Intervention*). In addition to phone calls, CHWs will also contact patients via a secure NYULMC phone through text messages to communicate study activities(see Text Message Script). CHWs will also work with partner agencies to conduct community-level activities, such as culturally tailored physical fitness classes and healthy cooking demonstrations, that patients will be invited to attend. The CHWs will make necessary referrals to other services available in the community (i.e. exercise classes, social services, mental health, tobacco cessation, etc.). CHWs will complete an *Encounter Report* to document unscheduled encounters with study participants (ie. such as when a participant calls the CHW to request referrals to services or to report an illness or new diagnosis.) In order to understand the COVID-related impact and needs of study participants in managing their health and to improve CHW referrals during the COVID19 pandemic, CHWs will complete a Rapid COVID Assessment via phone up to once per month or as needed (see study forms for: *Rapid COVID Assessment*, *Rapid COVID Assessment – Repeating Form*).

Multiple sessions will be hosted at varying times/days of the week to accommodate schedules of both working individuals and at-home caretakers. Small incentives will be provided throughout the intervention to encourage ongoing attendance, and incentives will be distributed at program completion for individuals who attended all 5 sessions.

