#### Consenting and data collection with waitlisted control participants

For control participants, the study will collect EHR data on clinical measures only that will be linked to a unique identifier housed at the primary care practices; there will be no survey data collection with control participants. In other words, the study will not be evaluating changes in study outcomes via non-EHR data among waitlisted control participants who receive the CHW intervention. For these reasons, we are requesting a waiver of authorization (see *Section IVb Process of Consent*). After completion of Round 1 intervention with intervention participants, CHWs will call contact waitlisted control participants regarding the group education sessions. Control participants will be offered the same content and dosage of education sessions.

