  - Height and weight data during the data collection period, Month and year of measurement
  - All lab results for: A1c, lipid profile during the study period, Month and year of measurement
  - All BP measurements (systolic and diastolic) during the study period, Month and year of measurement
  - Dates of clinic visits

De-identified claims data obtained from the Healthfirst data warehouse to be provided to the study team includes:

- All hospital admissions and ED visits during the intervention period (Study ID, Bill type, Encounter type, Admission Month/Year, Length of stay, DRG, Primary ICD 9/10 diagnosis code, Secondary diagnosis codes, if available, ICD 9/10 procedure codes, Attending physician specialty, Allowed Amount, Discharge status, Admit type, Admit source)
- Pharmacy claims (Study ID, Drug generic names, Drug class, Dates of Fill (month/year only), Total Drug Cost Amount)
- Outpatient claims (Study ID, Primary ICD 9/10 diagnosis code, Secondary diagnosis codes (up to 5), if available, ICD 9/10 procedure codes, Allowed Amount, Month/year of claim, Physician specialty)
- Lab claims (Study ID, Allowed amount, Month/year of claim, Type of test)

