## B. Data Analysis and Data Monitoring

### B1. Aim 1 Analysis

AIM 1: To compare the effect of the EHR/CHW intervention with usual care on weight loss. The primary outcome will be probability of eligible patients at a PCP to lose 5% or more of their body weight six months following the index office visit.

Secondary outcomes include: Average reduction in HbA1c, % sustained >5% weight loss at 12 months; improved lipids and blood pressure 6- and 12- months following the index office visit.

*Hypothesis:* Individuals receiving care during the implementation of the EHR/CHW intervention will be more likely to lose 5% of their body weight six months following the index office visit than individuals receiving care as usual. This will translate directly to a commensurate increase in the proportion of the study sample under the EHR/CHW intervention losing 5% of their body weight relative to the care as usual group.

The analysis of the effect of EHR/CHW on the outcome measure will be based on a Generalized Linear Mixed Model (GLMM). In particular, we will use a random effects model that assumes a binomial

distribution with a logit link function. The comparison will make no linear assumption about the time trend for each outcome over the course of the trial. The model will be as follows:

$$(1) \quad \text{logit}(Y_{ijt}) = \mu + \alpha_j + \theta_t + \tau C_i,$$

where  $Y_{ijt} = 1$  if the  $i^{\text{th}}$  subject attached to the  $j^{\text{th}}$  site at time quarter  $t$  loses 5% or more her body weight six months following the index visit,  $Y_{ijt} = 0$  otherwise.  $\alpha_j$  is a random effect for site  $j$  with mean 0 and variance  $\sigma_b^2$ .  $\theta_t$  is a time-specific effect a quarter  $t$ ,  $t \in (1, 2, \dots, 12)$ .  $C_i$  is an indicator variable, and  $C_i = 1$  if individual  $i$  receives care under the EHR/CHW intervention,  $C_i = 0$  if individual  $i$ .  $\tau$  represents the treatment effect of the intervention. The model will be fit using the LME4 package using R software. The hypothesis will be tested using two-sided level of significance  $\alpha = .05$ . Because outcome data will be derived from administrative data, we do not anticipate missing data. However, in the event that there is missing data, we will use multiple imputation under the assumption of data missing at random (MAR). This is consistent with following intent-to-treat protocol.

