**4. Cost-Effectiveness/Sustainability:** What were the costs of the integrated intervention to the insurer organizations and physician practice and did these additional costs provide added value at patient and provider levels? What were the net costs and benefits of different combinations of CHW and EHR interventions?

Using average resource utilization and costs per patient (in first 6 and 12 months of follow-up), we will compare resources incurred by the trial arms during the follow-up period at each time point. Our outcome will be the incremental cost per person achieving 5% weight loss. Cost data will be used to inform HF leadership of program costs for consideration of sustainability of CHW models by payer organizations.

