#### **G. Documentation of Consent**

### *Intervention Participants*

Study staff will obtain consent and HIPAA authorization by reading the verbal informed consent script to the subject to introduce the study and will then proceed to obtain verbal consent by reviewing the Consent Brochure with the participant. The participant will be given adequate opportunity to review and clarify questions before verbally consenting. The subject will receive a mailed copy of the Consent Brochure. A translated verbal Telephone script will be used for non-English speaking subjects, depending on their preferred language(upon approval of the *Waiver of Authorization and Documentation of Consent*, translated documents will be uploaded via a subsequent modification).

Study staff who have obtained the verbal consent will document the consent and the date of consent on a secure REDCap database. The REDCap database tracking form is the only record linking a participant's name and Subject ID.

Signed informed consent forms from participants consented in earlier versions of the protocol will be stored in a separate folder in a locked cabinet accessible only to study staff.

Patient survey data will be collected at baseline and at 6-months follow-up to evaluate the effectiveness of the CHW intervention. EHR data will be used to generate a registry of eligible participants for recruitment. EHR data will also be used to compare clinical outcomes (e.g., height and weight). EHR data will be collected at baseline, 6-months and 12 months. The informed consent for intervention participants will outline elements of the EHR data collection, CHW group education, one-on-one counseling, survey data collection, and Healthfirst claims data collection.

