### *Control Participants*

The study will only collect EHR data from control participants and will not collect survey data or claims data. A Waiver of Authorization is being requested for EHR data collected from control participants (see *Application for Waiver of Authorization for Consent Participant EHR data*). Without the requested waiver, the study could not be practically carried out and would adversely affect the scientific rigor of the study. Although control participants will be offered the full CHW intervention at a later time point (i.e., waitlist control), experience from similar studies have shown that recruitment and retention of control participants would dramatically increase the CHW caseload. The study is only collecting clinical outcomes from control participants through the EHR and this data will be de-identified. All variables for extraction will be pre-approved by all participating PCPs. MOUs between PCPs and NYU will explicitly outline the process of de-identification of the data and the list of variables for extraction.

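### The cost-effectiveness analysis compares care costs between arms, but the plan gives no cost source for the control arm

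*Combined protocol and SAP*

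**What the plan says.** Section III.B2, item 4 (Cost-Effectiveness/Sustainability) takes mean resource use and mean cost per patient over the first 6 and 12 months of follow-up. It then says "we will compare resources incurred by the trial arms during the follow-up period at each time point". The outcome is an incremental cost for each person who reaches 5% weight loss. The item also asks about the net costs and benefits of alternative mixes of the CHW and EHR components, and says that the cost data will tell the insurer's leadership what the programme costs.

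The data sections say the following.

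- Section VI.G, Control Participants: "The study will only collect EHR data from control participants and will not collect survey data or claims data".
- Section I.C2, on waitlisted controls: "the study will collect EHR data on clinical measures only".
- Section VI.G, Intervention Participants, lists what the intervention consent covers, including "one-on-one counseling, survey data collection, and Healthfirst claims data collection".
- Section III.A2 lists the Healthfirst claims extract without naming an arm. It begins with "All hospital admissions and ED visits during the intervention period" and goes on to pharmacy, outpatient and laboratory claims, with allowed amounts or drug costs.

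**The concern.** An incremental cost is a difference between two arm means. If one arm's care cost is not collected, the analysis as written cannot be run. The analyst would have to choose later between a programme-cost ratio, a costing built from EHR items, and a claims summary in one arm. These answer different questions, and only the first two compare the arms at all.

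The result has an audience. The Contributions text in section I presents cost calculation as one of the study's innovations, in support of reimbursement, and item 4 sends the cost data to the payer. A choice made after the data are seen would weaken that use.

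**Working it through.** The documents give no cost, ratio or economic sample size, so there is no figure of the plan's own to reproduce. The check sets what the analysis needs beside what is collected.

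**What the ratio needs**

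Ratio = (mean cost, intervention − mean cost, control) / (proportion with 5% loss, intervention − proportion with 5% loss, control).

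| Term | Stated source |
|---|---|
| Proportion with 5% loss, both arms | EHR weight (III.A2) |
| Care cost, intervention | Healthfirst claims (III.A2; consent in VI.G) |
| Care cost, control | None: claims excluded (VI.G), EHR clinical measures only (I.C2) |
| Programme cost | None listed; I.C2 describes CHW contacts, not their cost |

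**Size of the gap**

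- Section III.B1, Power Calculation: 1040 participants, evenly randomised, so 1040/2 = 520 controls.
- Figure 1 and the Sampling paragraph of III.B1 give 960 instead. If evenly split, 960/2 = 480 controls.
- Planned claims coverage of controls is zero on either total.

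**Could another source fill it?** The EHR extract in III.A2 covers both arms and includes visit dates, medications and laboratory results. It has no cost field, admissions or emergency visits, and no unit-cost method is given. The warehouse utilisation files in III.B2, item 1 record clinicians' use of the alert and registry functions, not patient costs.

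**Are the intervention-arm claims complete?** The patient eligibility criteria in section II do not require Healthfirst membership, so claims may be missing for some intervention participants too.

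**Time origin.** Item 4 does not say when follow-up starts. Section III.B1 defines the primary outcome as the probability that patients "lose 5% or more of their body weight six months following the index office visit", but the index visit is not defined. Section II accepts a routine visit and an HbA1c test at any time in the previous 12 months. If the index visit were that qualifying visit, CHW costs could fall partly or wholly outside the six-month window. Sections I.C1 and VI.G schedule EHR extraction at baseline, 6 and 12 months, which is another possible clock.

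**Control exposure by 12 months.** Section I.C1 offers controls the sessions in the second six-month round. The waitlist paragraph of I.C2 says after Round 1. The CHW Protocol paragraph of I.C2 and section VI.A say after the intervention rounds, in the plural. On the first two readings, controls may have received the programme before 12 months.

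**Mixes of components.** Section III.A1 puts a minimum set of components, including the EHR alert and registry, in every participating practice. Section I.C1 randomises individuals within practice. No group receives a different mix, so the net cost and benefit of alternative mixes cannot be estimated from this design.

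**The case against.** The strongest reply is that item 4 is mainly about programme cost. Its first question concerns what the intervention costs the insurer and the practices, and its last sentence speaks of programme costs. Neither needs control claims. This stands in part: the programme-cost purpose survives. But the sentences between them promise mean resource use and cost by arm, and even a programme-cost reading has no listed source.

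Second, the claims list in III.A2 names no arm, so it might be meant to cover controls. The explicit statement on controls is in VI.G, and it excludes claims. The sections need reconciling.

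Third, EHR visits, laboratory tests and medications could be priced for both arms, or the control waiver could be extended to claims. Either would stay closer to the planned contrast. Both are possible, but neither is in the plan, and EHR pricing would still omit hospital and emergency use.

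Fourth, this is an Aim 2 item with no hypothesis test attached. That is correct and limits the seriousness of the point.

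**Conclusion.** The concern holds for the between-arm comparison of care use and cost. As written, it cannot be formed, because planned claims coverage is 0 of about 520 controls (or 480 on the 960 total) and no other priced source is stated. It should be fixed. This rests on taking the VI.G statement on controls as governing and on no costing method appearing elsewhere in the documents.

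A reader might infer more than the documents support:

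- *That the economic analysis fails altogether.* It does not. Weight response is available in both arms, and a programme-cost ratio can be built once a cost source is named.
- *That nothing is known about control utilisation.* Office visits, laboratory results and medications are in the EHR extract for both arms.
- *That the bias in the ratio can be sized.* With no cost amounts in the documents, it cannot.
- *That the scheduled contacts fix the programme cost.* Section I.C2 plans "5 monthly 90-minute group health education sessions" and says "patients will receive up to 9 follow-up phone calls from CHWs", but this is no ceiling on CHW work. Recruitment calls, COVID assessments by phone, unscheduled encounters and monthly team meetings come on top.
- *That the primary result is at risk.* The weight-loss analysis uses EHR data from both arms and does not depend on claims.

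**What to change.** Reconcile III.A2, III.B2 item 4 and VI.G, and rewrite item 4 as follows.

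1. Restate the outcome as incremental programme cost per additional person achieving 5% weight loss at six months, with arms compared as randomised. Count CHW delivery plus the EHR and practice costs attributable to the intervention. Say how alert and registry costs shared by both arms within a practice are attributed.
2. Name the cost source, for example CHW contact records priced with programme staff costs.
3. State that claims are summarised in the intervention arm only, that they may be incomplete because Healthfirst membership is not an eligibility criterion, and that utilisation offsets are not compared between arms.
4. Define one time origin and use it for both cost and weight loss.
5. Reconcile I.C1, I.C2 and VI.A on when controls are offered sessions. If that is before 12 months, do not present the 12-month contrast as intervention versus no programme.
6. State that the net costs and benefits of alternative CHW and EHR mixes cannot be estimated from this design.

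The cost is a wording change plus modest costing work. The downside is a narrower economic claim that says nothing about hospital, emergency department or other utilisation offsets.

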#### *Provider Survey*

The data will be tabulated and summarized descriptively to address research questions and to assess change in attitudes from baseline to 12 months. All quantitative data will be entered and analyzed in SPSS.

#### *Key Informant Interviews*

Interview data will be transcribed and analysis transcribed data will follow "constant comparison" analytic approach. The "constant comparison" approach is a method of explanation building in which the findings of an initial case are compared to a provisional category, property or proposition, revised as

necessary and then other details or new cases are then compared against the revision and revised again as needed. This process is continued until an area of interest is fully explicated, reaching theoretical saturation. Using "thematic" coding, we will develop an initial set of codes, which will be reviewed by the community-clinical coalition to ensure they are relevant and complete. For each core code, we will ultimately develop one or more "secondary codes" that represent either more specific or restricted aspects of the phenomenon, to contextualize it, or to suggest underlying meanings. The secondary codes will vary in specificity or subtlety depending on the judged substantive value of additional refinements. Transcripts will be coded by at least four coders. Discrepancies in coding will be discussed and resolved, then the process is repeated with a new set of transcripts until an acceptable level of inter-coder reliability between them has been achieved, estimated using an appropriate chance-corrected statistic (e.g., kappa for nominal data and T-index for ordinal data). The coded transcripts will be analyzed with *Atlas.ti*, a software package for qualitative data analysis. Analysis will be conducted to inform best practices for scalability that can be replicated by payer organizations and health care systems.

### **C. Data Storage and Confidentiality**

Confidentiality will be maintained for participants according to mandatory Institutional Review Board regulations, under the supervision of [name].

#### *EHR-CHW Intervention*

As described above, all patient data will be de-identified prior to transfer to a NYU MCIT managed network databases via a secure sftp site. All computer systems are protected from possible external access. No internet access is possible with the research systems.

#### *Intervention Participants and Provider Survey Data*

To safeguard confidentiality and anonymity, unique identifiers will be assigned to all participants for all portions of the study and all data collection instruments will identify participants only by these unique identifiers. On the baseline and follow-up surveys, the first page of the survey will ask participants for updated contact information so that CHWs can maintain contact throughout the intervention period. Data will be entered into REDCAP, a HIPPA-compliant a research database platform, by a study staff member and alldata will be housed on a secure MCTI managed network drives. Pages containing participants name and contacts information and logs linking subjects' identifying information to study numbers will be kept locked in a subject file per IRB regulation in a file cabinet in a secure location. Baseline and followup survey data will be kept in individual subject files per IRB regulation. Contact information from consented participants will be kept on file for the duration of the trial and will be destroyed (both electronic and hard copy) upon the dissemination of trial results (approximately 5 years).

